## Measures and Outcomes

The primary outcome measures will be those that informed the multi-domain quality of life measure utilized in the original REACH II randomized clinical trial. This approach is similar to that used by Nichols and colleagues in two REACH VA studies. Burden is considered the signature outcome since it is used for power and sample size estimates for analysis purposes.

### Measures include:

- Burden: A 12-item version of the Zarit Caregiver Burden Interview. Each item represents a statement related to some aspect of perceived burden. Caregivers rate each item with higher scores indicating higher rates of burden.
- Depression: A 10-item version of the Center for Epidemiological Studies Depression Scale. Each item represents a statement for which respondents indicate how often in the past week they have felt that way in the past week. Total score is computed by summing scores for all items with higher scores indicating higher levels of depressed symptoms.
- Social support: Two subscales of Social Provision Scale (8 items), Reliable Alliance and Guidance will be used to assess availability of support and satisfaction with support from others.
- Self-rated health: A single item of caregiver's perception on his/her own health is included.
- Interactions with health care providers: Medical care management and coordination is measured with a 9-items of NSOC survey for how caregivers manage medical needs for care recipients and provide substantial help with health care activities including interaction with health care providers.

Additional outcome measures will include those that capture a more diverse aspect of dementia care than capture by the QoL REACH II measure and include:

- Caregiver stress: Perceived Stress Scale is a 10-item classic stress assessment, designed to help measure individual stress levels. Individual scores on the PSS can range from 0 to 40 with higher scores indicating higher perceived stress.
- Positive caregiver: Positive Aspect of caregiving (PAC) is measured with eleven items of the favorable aspects of their caregiving experience. The items ask about their mental or affective state related to their caregiving experience, for example, providing help to care recipients has 'made me feel more useful', 'made me feel strong and confident', 'given more meaning to my life', 'enabled me to develop a more positive attitude toward life', and 'enabled me to learn new skills'.
- Cognitive change in care-recipient: A 12-item self-administered questionnaire (NPI-Q), completed by the caregivers about patients for whom they care, that measures the presence and severity of 12 Neuropsychiatric Symptoms (NPS) in patients with dementia, as well as the caregiver's distress.
- Additional process measures will be generated from user logs of the systems to document treatment implementation, including the total duration of time spent on GamePlan4Care. A program evaluation measure, the USE questionnaire, will be provided to caregivers after completion of the 6-month battery has been administrated. The USE questionnaire consisting of 30 items on usefulness, ease of use, ease of learning, and satisfaction will evaluate participant's attitude toward GP4C system.

For participants whose care recipient has passed in the last 6 months, caregiver burden and cognitive change in care recipient will not be assessed at 6 months .

## Data Analysis

Caregiver participants will be randomized to the two intervention arms (GP4C and R4C) with the ratio of 1:1. Primary and secondary outcomes, including the Zarit's caregiving burden interview, will be assessed at baseline and 6-month follow-up. Covariates in the analysis include demographic characteristics of the caregivers.

Common descriptive statistics (mean, standard deviation, median, interquartile range for continuous variable; frequency and percentage for categorical variables) will be calculated for all covariates in each intervention arm and the two arms will be compared at baseline. Goals of our statistical analysis will be to evaluate the effectiveness of each intervention arm and to compare the two arms. For each intervention arm, the difference between 6-month follow-up and baseline will be computed. Paired t-test and Wilcoxon signed-rank test will be used to detect significant changes in outcome variables at 6-month follow-up since the baseline. Medians, means, and 95% confidence intervals of the differences will be calculated using both empirical percentiles and normal approximation. The two intervention arms will be compared at each follow-up time and for the whole trial period. We will compare the two arms at 6-month follow-up using the two-sample t-test and Wilcoxon rank sum test for each of the two outcomes.

The Anderson-Darling test will be used to check the normality assumption at baseline and follow-up times for the two outcome variables. If normal assumption is significantly violated then only nonparametric estimates and tests (i.e., median, IQR, empirical confidence intervals, Wilcoxon signed-rank test, and Wilcoxon rank sum test) will be reported, and data transformation, such as log and square root transformations, will be considered to normalize the outcome variables for further model-based testing. The two arms will also be compared incorporating observations baseline and the two follow-ups in longitudinal analysis of covariance (ANCOVA) models having the follow-up time and adjusting for covariates.

Given the fact that participants will be randomized into the two arms, the outcome variables will likely be comparable between the two arms at baseline. As a result, the interaction effect between the treatment arm and follow-up time (while adjusting for covariates) will be tested in the longitudinal analysis to evaluate the difference between the two intervention arms because a significant interaction indicates the caregiver's outcome has followed significantly different trajectories in the follow-up period depending on the treatment arm. Missing values may be possible because 1) some caregivers may be lost to follow-up, and 2) some caregiving recipients can be deceased prior to the follow-up. Missing patterns will be inspected and multiple imputation methods, including regression imputation, propensity score imputation, and MCMC imputation will be considered based on the missing mechanism^47. All tests will be two-sided and a p-value less than or equal to 0.05 will be reported as statistically significant. Statistical Analysis Software (SAS software, version 9.4; SAS Inc., Cary, NC) will be used to conduct the proposed analysis.

### Sample size considerations

The primary endpoint in this power analysis is the Zarit's caregiving burden score. Assuming 20% attrition rate at the 6-month follow-up, we plan to initially enroll totally 240 family caregivers who will be equally randomized into two will be equally randomized into two arms (120 per arm), and we expect a minimum of 100 caregivers per arm to complete the 6-month assessment. The sample size of 100 in each arm can guarantee 80% power at significance level 0.05 to detect the effect size of 0.28 standard deviation (SD)

difference between baseline and 6 months follow-up in a two-sided paired t-test. (See Table 4). Nicholas et al. reported the effect size of 0.33SD of Zarit's score from the REACH VA intervention (also between baseline and 6-month follow-up). While GP4C will use a different delivery strategy than used in the REACH II and REACH VA trials, core therapeutic materials and techniques of the intervention are maintained. Thus, we expect GP4C to have a similar impact on caregiver outcomes as observed in prior REACH II trial. Thus, we conclude that enrolling 120 caregivers per arm (100 available at 6 months) will achieve sufficient statistical power to detect the effectiveness of the proposed interventions, even if the GP4C full functionality intervention is slightly less robust than the original REACH interventions.

*Table 4. Sample size and power by effect size*

Effect size of 0.28 standard deviation (SD) difference		Effect size of 0.33 standard deviation (SD) difference	
Sample Size	Power	Sample Size	Power
70	.646	70	.777
80	.706	80	.830
90	.757	90	.872
100	.800	100	.905
110	.834	110	.929
120	.868	120	.948
130	.893	130	.962
140	.914	140	.972
150	.931	150	.980

## Refinement for Future Testing and Dissemination

While Aim 1 usability testing will yield the in-depth feedback needed to produce the best possible version of the GP4C system for testing in the field, 3.5 years of testing to achieve Aim 2 will also produce a considerable amount of feedback regarding its functionality and utility. In order to realize the full value of the project, feedback from GP4C users during Aim 2 project activities (including community partners, interventionists, and caregiver participants) will be used during a final round of iterative design and system updates by the Baylor Scott & White Office of Digital Health. These updates are judged to be critical as they will best position the GP4C for ongoing clinical trials, future cultural adaptations, and eventual dissemination to CBOs.

## Timeline of Study Activities

Aim and Activity	Year 1				Year 2				Year 3				Year 4				Year 5			
	Q1	Q2	Q3	Q4																
Aim 1: Prepare GP4C for Testing in a RCT																				
• GP4C System Import & Integration w/BSWH IT Systems																				
• Digital Health Team UI/UX Review and Updates																				
• Engage Community Partners for CG Usability Testing																				
• Usability Testing with Dementia Caregivers																				
• External Advisory Committee Review																				
Aim 2: Randomized Clinical Trial of GP4C																				
• Recruitment Materials Development																				
• Engage Program Champion within Community Partners																				
• Interventionist Training																				
• Participant Recruitment & Screening & Consent																				
• Intervention Delivery																				
• Participant 6-month Reassessment																				
Project Completion																				
• Data Analysis																				
• External Advisory Committee Review Preliminary Findings																				
• Post study refinements to GP4C system																				
• Final Report Preparation & Dissemination of Findings																				

## Alternative approaches

Successful completion of the two AIMs of this study will advance a proof of concept that the REACH II intervention can be made available online to caregivers and that the burden of intervention delivery can be lessened with web technologies that automate many of the tasks that required human resources. This will fill a significant gap in the availability of online evidence-based services for caregivers. It will not, however, be the only online resource for caregivers. Alzheimer's Navigator® is a content navigation tool that takes user responses to survey questions to direct them outside the site to relevant educational content, mostly related to the planning and provision of care for the care recipient. GP4C provides individual feedback, and link users to internal, tailored content for skill-development related to caregiver self-care and dementia care management. The intervention includes an integrated live-support element with regular interventionist outreach for coaching sessions to facilitate skills acquisition and problem-solving.

Access to the BSWH Office of Digital Health is a significant and unique asset to this project, allowing us to bring GP4C in-house for UI/UX (and hosting). While there are commercial usability laboratories, using resources within the BSWH system provides a more cost-effective approach and ensure secure hosting during the testing phase. We have allotted one year for this process that we believe is reasonable. The BSWH Digital Health Office is committed to having a product within a year.

Recruitment is often a challenge in caregiving studies. [name] and [name] have a long and strong record of completing research trials as expected. Moreover, [name] has worked closely with the partner CBOs on number projects. Establishing a "champion" within the organizations will demonstrate our mutual commitment to project success. While our monthly recruitment goals are reasonable given the target recruitment area, BSWH is the largest not for profit healthcare provider in Texas, and we can expand recruitment internally if needed.

## 1 Overall Summary from ClinicalTrials.Gov

Daily care and supervision of a person living with dementia (PWD) has been defined as "intense caregiving" and is associated with significant daily burdens and an overall threat to the caregiver's quality of life. Despite evidence suggesting that negative consequences can be remediated with community-based supports, those services remain elusive to caregivers due to the systemic challenges of turning interventions into services. This study is based on a practical approach of applying technology to an existing evidence-based intervention, Resources for Enhancing Alzheimer's Caregiver Health II (REACH II), refined with real-world user feedback and rigorously tested to create an online family caregiver support system that has the potential of both scalability and sustainability. This two-group randomized controlled trial will compare the relative impact of GP4C to an education-based online site called Resources4Care (R4C) on a wide range of family caregiver outcomes. Family caregivers will be randomized to one of the two conditions and will complete an assessment battery at baseline and at the 6-month follow-up.

## 2 Specific Aims

Family care of an older adult is a valued tradition of society and has become an essential element of the US healthcare system with 83% of long term care provided to older adults coming from family members or other unpaid helpers. As the population of older adults grows, almost doubling in size from 2012 to 2040^2, so too will the expectations placed on American families. This is especially true of families who support community living for individuals living with Alzheimer's disease and related dementias (ADRD), which has been defined as "intense caregiving" and is associated with significant daily burdens and an overall threat to the caregiver's quality of life. A robust body of ADRD research demonstrates that interventions aimed at supporting and educating caregivers can significantly improve the quality of care delivery and improve the well-being and quality of life for both caregivers and persons with dementia (PWD). Despite the fact that over 200 interventions have been found to be effective for dementia caregivers in randomized clinical trials (results confirmed in 7 meta-analyses and 17 systematic reviews), only six have undergone translation efforts resulting in publication. The lack of credible translation of evidence-based interventions into widely available community-based services means that the clear majority of the current 16.1 million family caregivers do not have access to evidence informed long term care supports and services. Thus, *family caregivers remain at risk of the known negative consequences of caregiving despite evidence suggesting that those negative consequence can be remediated*. There is an immediate and critical need to address this issue which is of significant societal impact.

This study is based on a practical approach of applying technology to an existing evidence-based intervention, Resources for Enhancing Alzheimer's Caregiver Health II (REACH II), refined with real-world user feedback and rigorously tested with the goal of creating an online family caregiver support system that has the potential of both scalability and sustainability. The feasibility of our proposition has been established by the creation of the proof-of-concept system **GamePlan4Care (GP4C)**, demonstrating that modern internet technology can be used to automate key components of REACH II delivery. Such automated REACH II components include active engagement of caregivers in skill-building to address diverse challenges in caregiving and flexible tailoring of the intervention based on participant needs. **Therefore, GamePlan4Care is positioned for a Phase 1 study to incorporate the full breadth of REACH II material and optimize the user experience for efficacy testing in a randomization clinical trial that engages BSWH clinics and community-based organizations (CBOs) where family caregivers already seek services.**

**Two specific staged AIMS are proposed in this study.**

**AIM 1. Advance the current proof-of-concept GP4C into a viable delivery system for the REACH II intervention.** Further development will include uploading the full breadth of REACH II education and skill-building materials, usability testing and updates to the user interface/user experience (UI/UX), creating a portal of delivery tools used by Dementia Care Specialist (DCS; i.e., interventionist), and establishing a comparable education-focused online system (Resources4Care; R4C) to be used in comparison to the multicomponent, skills-training GP4C system. Development activities will be conducted by the Baylor Scott & White Health (BSWH) Office of Digital Health with engagement of community-based organizations, family caregivers, and external advisors, with oversight by the GP4C research team.

**H1:** *Within 12 months of usability testing with 32 family caregivers, the GP4C research team will reach consensus with the BSWH Office of Digit Health and an external Advisory Committee that GP4C is a viable platform for online delivery of REACH II with R4C as an appropriate comparison condition.*

**AIM 2. Compare the relative impact of GP4C and R4C, both of which include access to a Dementia Care Specialist, on a wide range of family caregiver outcomes.** Family caregivers will be randomized to one of the two conditions and will complete an assessment battery at baseline and at the 6-month follow-up. Primary outcome measures will include burden, depression, social support, and caregiver's health and interaction with health care providers. Secondary outcomes will include caregiver stress, positive aspects of caregiving (PAC), cognitive change in care-recipient. The CBOs will designate a "GP4C Champion" to promote the enrollment of 240 family caregivers who have computer access and report regular use of the internet. Use of GP4C & R4C and contact with DCS will be recorded by the system as implementation data.

**H1:** *Family caregivers randomized to the GP4C condition will report greater improvement on primary and secondary outcomes as compared to family caregivers in the R4C condition.*

*GP4C will fill a critical gap in caregiver support services as an evidence-based, internet-enabled system capable of providing immediate, tailored education and skills training to caregivers who can access live support from a DCS via phone or web-based video. Compared to existing evidence-based interventions, CBOs will face fewer barriers to scaling and sustaining GP4C, a critical achievement in efforts to serve the growing number of family caregivers who face the challenges of dementia caregivers.*

***This Statistical Analysis Plan is limited to AIM 2,  
a Phase 1 study of two dementia caregiver interventions.***

### 3 Summary of the Two Study Groups

- Experimental: GamePlan4Care (GP4C)
  - Participants in this arm will have access to full functionality and content of the online system GamePlan4Care (GP4C) including educational resources, skills training, and support tailored to their unique caregiving needs. Additional individualized feedback will be automatically generated based on responses to online questions and will include links to relevant site educational/skill-building content. Participants will be assigned a Dementia Care Specialist who will facilitate caregiver interactions with the online material and provide skills training via telephone or web-video conference. Study participants assigned to GP4C will receive 9 automated emails and 4 phone calls over a 6-month period.
- Active Comparator: Resources4Care (R4C)
  - Participants in this arm will receive access to Resources4Care (R4C), a feature-limited version GamePlan4Care system. R4C will serve as an online hub for articles and videos about Alzheimer's disease and dementia. Educational topics will include information on: 1) Alzheimer's Disease & Dementia, 2) Caregiving, 3) Caregiver Stress and 4) Home Safety. R4C will present a page on each topic with active links to two additional online sources on the same topic. Study participants assigned to R4C will receive two emails from their DCS encouraging the caregiver to review specific education materials. Each email will be followed by brief "check-in" calls (15-min each) at three months and five months after randomization.

## 4 Entry Criteria

### 4.1 Inclusion Criteria

- Must be age 18 years or older
- Providing at least 8 hours of weekly care and/or supervision (on average) for a friend or family member with a self-reported diagnosis of Alzheimer's disease or a related dementia. Family will be subjectively determined by the caregiver to enable a broader definition of a "family" member often found in minority communities (e.g., a person not related by blood but who serves in the role of an "aunt" or "grandchild").
- The family member, named as the care recipient (CR) in this proposal, must be diagnosed with AD/ADR (self-report from the caregiver accepted) and is experiencing signs of dementia as verified by the family caregiver on the AD8 informant interview. A score of 2 or greater is the inclusion criteria.
- Must demonstrate access to a home computer with internet access to research staff and report using the computer to access the internet at least three times per week, on average.
- English-speaking caregivers
- Must reside within the recruitment area (Target counties within Texas: Bastrop, Bell, Blanco, Burnet, Caldwell, Coryell, Fayette, Hamilton, Hays, Lampasas, Lee, Llano, Milam, Mills, San Saba, Travis, Williamson)

### 4.2 Exclusion Criteria

- Current participation in another caregiving evidence-based program
- Previous participation in usability testing for current system development

### 4.3 Sample Size Considerations

The primary endpoint in this power analysis is the Zarit's caregiving burden score. Assuming 20% attrition rate at the 6-month follow-up, we plan to initially enroll totally 240 family caregivers who will be equally randomized into two will be equally randomized into two arms (120 per arm), and we expect a minimum of 100 caregivers per arm to complete the 6-month assessment. The sample size of 100 in each arm can guarantee 80% power at significance level 0.05 to detect the effect size of 0.28 standard deviation (SD) difference between baseline and 6 months follow-up in a two-sided paired t-test. (See Table 4). Nicholas et al. reported the effect size of 0.33SD of Zarit's score from the REACH VA intervention (also between baseline and 6-month follow-up). While GP4C will use a different delivery strategy than used in the REACH II and REACH VA trials, core therapeutic materials and techniques of the intervention are maintained. Thus, we expect GP4C to have a similar impact on caregiver outcomes as observed in prior REACH II trial. Thus, we conclude that enrolling 120 caregivers per arm (100 available at 6 months) will achieve sufficient statistical power to detect the effectiveness of the proposed interventions, even if the GP4C full functionality intervention is slightly less robust than the original REACH interventions.

*Table 4. Sample size and power by effect size*

| Effect size of 0.28 standard deviation (SD) difference |       | Effect size of 0.33 standard deviation (SD) difference |       |
|--|-------|--|-------|
| Sample Size  | Power | Sample Size  | Power |
| 70   | .646  | 70   | .777  |
| 80   | .706  | 80   | .830  |
| 90   | .757  | 90   | .872  |
| 100  | .800  | 100  | .905  |
| 110  | .834  | 110  | .929  |
| 120  | .868  | 120  | .948  |
| 130  | .893  | 130  | .962  |
| 140  | .914  | 140  | .972  |
| 150  | .931  | 150  | .980  |

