## 6 Statistical Methods and Analyses

Caregiver participants will be randomized to the two intervention arms (GP4C and R4C) with the ratio of 1:1. Primary and secondary outcomes, including the Zarit's caregiving burden interview, will be assessed at baseline and 6-month follow-up. Covariates in the analysis include demographic characteristics of the caregivers. Common descriptive statistics (mean, standard deviation, median, interquartile range for continuous variable; frequency and percentage for categorical variables) will be calculated for all covariates in each intervention arm and the two arms will be compared at baseline. Goals of our statistical analysis will be to evaluate the effectiveness of each intervention arm and to compare the two arms. For each intervention arm, the difference between 6-month follow-up and baseline will be computed. Paired t-test and Wilcoxon signed-rank test will be used to detect significant changes in outcome variables at 6-month follow-up since the baseline. Medians, means, and 95% confidence intervals of the differences will be calculated using both empirical percentiles and normal approximation. Multiple comparison adjustments, e.g., Holm-Bonferroni method and Hochberg procedure, will be implemented to control the family wise error rate when testing multiple outcome measures in Section 5.

The two intervention arms will be compared at each follow-up time and for the whole trial period. We will compare the two arms at 6-month follow-up using the two-sample t-test and Wilcoxon rank sum test for each of the two outcomes. The Anderson-Darling test will be used to check the normality assumption at baseline and follow-up times for the two outcome variables. If normal assumption is significantly violated then only nonparametric estimates and tests (i.e., median, IQR, empirical confidence intervals, Wilcoxon signed-rank test, and Wilcoxon rank sum test) will be reported, and data transformation, such as log and square root transformations, will be considered to normalize the outcome variables for further model-based testing. A pre-post analysis will be conducted to model the outcomes at 6-month follow-up to test the intervention arm and covariates adjusting the baseline measurements. The two arms will also be compared incorporating observations from baseline and follow-up in longitudinal analysis of covariance (ANCOVA) models or linear mixed-effects models having the follow-up time and adjusting for covariates.

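### Twenty percent attrition from 120 per arm leaves 96 completers, not a minimum of 100, so the plan's paired-test power at 0.28 SD is about 78%, not a guaranteed 80%

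*SAP*

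**What the plan says.** SAP 4.3 and the protocol section on sample size considerations carry the same text. The starting point is "Assuming 20% attrition rate at the 6-month follow-up, we plan to initially enroll totally 240 family caregivers", split equally into 120 per arm, which matches the 1:1 allocation in SAP section 6. The next statement is "we expect a minimum of 100 caregivers per arm to complete the 6-month assessment".

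Power is then attached to that count: "The sample size of 100 in each arm can guarantee 80% power at significance level 0.05", for a change of 0.28 SD in Zarit burden between baseline and 6 months, tested with a two-sided paired t-test. Table 4 lists power of .757 at n = 90 and .800 at n = 100 for 0.28 SD, and has no row between them.

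The closing sentence of the section repeats the count: "enrolling 120 caregivers per arm (100 available at 6 months) will achieve sufficient statistical power". The figure of 100 therefore appears three times in each document's argument: as the expected minimum, as the basis of the power statement, and in the conclusion.

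**The concern.** Enrolment, attrition and completers are three linked numbers, and any two fix the third. Here the third does not follow from the other two. Because 100 is called a minimum, rounding does not explain it: the expected count under the plan's own assumption lies below the stated floor.

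The guarantee of 80% power is calculated at 100, so it is not supported if the trial loses the proportion it says it will lose. Anyone monitoring retention against this section would also have two incompatible targets, 20% loss or 100 completers per arm.

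**Working it through.** **Inputs (SAP 4.3, same in the protocol):** 240 enrolled, 120 per arm; attrition 20%; two-sided α = 0.05; paired t-test; effect 0.28 SD, with 0.33 SD from the cited earlier trial as the alternative.

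**Step 1. Reproduce the plan's power at n = 100.**
- Normal approximation: power = Φ(d√n − 1.96) = Φ(0.28 × 10 − 1.96) = Φ(0.84) = 80.0%. Table 4 says .800.
- Exact calculation (noncentral t, n − 1 degrees of freedom, noncentrality d√n): 79.2%. On this basis n = 103 is the first size to reach 80%.
- At 0.33 SD the exact calculation gives 90.45%, against .905 in Table 4.

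The stated power therefore reproduces for the stated n, to within a percentage point whichever method is used.

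**Step 2. Check the completer count.**
- Expected completers = 120 × (1 − 0.20) = 96 per arm; 240 × 0.80 = 192 in total.
- Attrition implied by 100 of 120 = 1 − 100/120 = 16.7%.
- Enrolment needed for 100 completers at 20% attrition = 100/0.80 = 125 per arm, 250 in total.

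The count of 100 does not reproduce. It is 4 per arm too high.

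**Step 3. Power at 96 per arm.**

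| Method | n = 100 | n = 96 | Loss (points) |
|---|---|---|---|
| Normal approximation, 0.28 SD | 80.0% | Φ(0.28√96 − 1.96) = Φ(0.783) = 78.3% | 1.7 |
| Table 4, linear interpolation, 0.28 SD | 80.0% | .757 + 0.6 × (.800 − .757) = 78.3% | 1.7 |
| Exact noncentral t, 0.28 SD | 79.2% | 77.5% | 1.7 |
| Exact noncentral t, 0.33 SD | 90.45% | 89.3% | 1.2 |

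**Step 4. Detectable change with 80% power (exact t).** 0.283 SD at n = 100 and 0.289 SD at n = 96.

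**The case against.** The strongest reply is that the effect is trivial. Compared like for like, four fewer completers per arm cost 1.7 points of power. Setting the exact 77.5% against the stated 80% overstates the loss, because part of that gap is a difference of method or rounding that was already present at n = 100. This is right, and 78.3% is the figure to compare with Table 4.

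It can also be said that 0.28 SD is a cautious value. The plan expects an effect similar to the cited 0.33 SD, where power at 96 is 89.3%, so the conclusion that power is adequate for the paired test survives. This too stands. But 0.28 SD is the effect for which 80% is claimed, and it carries the argument that power holds if the online version works somewhat less well than its predecessors.

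Two other defences do not help. If 20% is read as a ceiling on attrition, the floor is 96, still not 100. Multiple imputation is only to be considered (SAP section 6), and the power statement rests on caregivers who complete the assessment; imputation does not create four more observed pairs.

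The true number with a burden score could be lower still, because the protocol's section on measures and outcomes says burden is not collected at 6 months when the care recipient has died. The documents give no death rate and do not say whether the 20% includes these caregivers, so this is an open question and not evidence of a further shortfall.

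**Conclusion.** The point holds. Under the plan's own 20% attrition, 96 per arm are expected at 6 months, not a minimum of 100, and power for the planned paired test at 0.28 SD is about 78% (78.3% on the basis comparable with Table 4, 77.5% by the exact t calculation). The size is modest: 4 caregivers per arm and about 2 percentage points, with 89.3% power remaining at 0.33 SD.

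The conclusion takes the plan's attrition rate, effect sizes and choice of a within-arm paired test as given. It also assumes that the 20% covers everyone without a 6-month burden score; if deaths of care recipients come on top, power is lower by an amount the documents do not allow one to calculate.

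**What to change.** In SAP 4.3 and the matching protocol section:

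- State 240 enrolled, 20% attrition, and 96 per arm (192 in total) expected at 6 months, both where the minimum is given and in the closing sentence.
- Add an n = 96 row to Table 4: .783 at 0.28 SD (interpolated from the present column) and .893 at 0.33 SD. Better, recompute the row with the software that produced the table.
- Replace the guarantee of 80% power with the power at 96.
- Say whether the 20% includes caregivers whose burden is not assessed because the care recipient has died.

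The cost is a few edited sentences and one table row in each document, with stated power about 2 points lower. No added enrolment is needed for this correction. Only if the sponsor wants to keep 100 completers at 20% attrition would enrolment have to rise to 125 per arm (250 in total), 10 more caregivers than planned.
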